## 4 Study Design

### 4.1 Description of Study Design

This is an open and off label use, interventional, single site study

### 4.2 Study Enrollment and Withdrawal

#### 4.2.1 Study Population

The HCWP Study eligibility are HCWs at high risk for SARS-CoV-2 exposure (eg MD/DO, NP, RN, and respiratory therapists in ED, Pediatric ED, Urgent Care, Pediatric Urgent Care and on Covid-19 units) at UNM HEALTH SYSTEM meeting all inclusion criteria.

#### Total number of participants: 350 (Group A and B)

- Group A: up to 275 (HCW who choose to be provided HCQ)
- Group B: up to 75 (HCW who choose not to be provided HCQ)

#### 4.2.1.1 Inclusion Criteria

1. Men or women  $\geq 18$  years of age who are UNM HEALTH SYSTEM health care workers and are asymptomatic for known presenting symptoms of SARS-CoV-2:
2. UNMHS HCWs include: MD/DO, NP, RN, and respiratory therapists working in ED, Pediatric ED, Urgent Care, Pediatric Urgent Care or on Covid-19 units. Study PI's will consider study enrollment of HCWs from other settings, for example certain outpatient clinics or inpatient units.
3. Are not positive for SARS-CoV-2 testing
4. Willing and able to comply with survey completion, scheduled visits, treatment plan, and other study procedures
5. Willing and able to provide informed consent

#### 4.2.1.2 Exclusion Criteria

Participants are excluded from the study if any of the following criteria apply:

1. Known hypersensitivity to HCQ or other 4-aminoquinoline compounds
2. Currently hospitalized
3. Symptomatic with subjective fever, cough, or sore throat
4. Current medications exclude concomitant use of HCQ, for example anti-arrhythmic agents, digoxin, cyclosporin, cimetidine, or tamoxifen.
5. Concomitant use of other anti-malarial treatment or chemoprophylaxis
6. History of retinopathy of any etiology
7. Psoriasis
8. Porphyria
9. Known bone marrow disorders with significant neutropenia (polymorphonuclear leukocytes  $< 1500$ ) or thrombocytopenia ( $< 100K$ )
10. Known liver disease
11. Known long QT syndrome
12. Use of any investigational or non-registered drug or vaccine within 30 days preceding the first dose of the study drugs or planned use during the study period. There may be some exceptions to requiring a 30-day washout that will be evaluated by the Co-Investigators on a case by case basis.

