#### **IND Exemption:**

- HCQ is lawfully marketed in the United States.
- The investigation is not intended to be reported to FDA as a well-controlled study in support of a new indication and there is no intent to use it to support any other significant change in the labeling of the drug.
- In the case of a prescription drug, the investigation is not intended to support a significant change in the advertising for the drug.
- The investigation does not involve a route of administration, dose, patient population, or other factor that significantly increases the risk (or decreases the acceptability of the risk) associated with the use of the drug product (21 CFR 312.2(b)(1)(iii)).
- The investigation is conducted in compliance with the requirements for review by an IRB (21 CFR part 56) and with the requirements for informed consent (21 CFR part 50)
- The investigation is conducted in compliance with the requirements of § 312.7 (i.e., the investigation is not intended to promote or commercialize the drug product).

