## 4.6 Participant Withdrawal or Termination

Reasons for early Withdrawal or Termination

- Participants become PCR-confirmed SARS-CoV-2 status
- Participant starts disallowed medication (Group A only)
- Advent of an adverse event which necessitates discontinuation of HCQ (Group A only, see section 6)
- Participant decides to withdraw from the study
- PI discontinues participation due to safety concerns
- Participant decides to withdraw consent
- Participant's primary care provider determines the study is not in participant's best interest
- PI decides to withdraw participant due to non-compliance

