#### 4.7.1.1 Dose Rationale

Hydroxychloroquine is a long-acting drug (elimination half-life:50 days). Loading dose of HCQ 600 mg has been administered for rheumatoid arthritis or systemic lupus erythematosus, with a usual maintenance dose 200 mg. Since the protocol will be used in HCWs with at high risk of exposure to SARS-CoV-2, the intent is to rapidly achieve an adequate drug level. For this study, we selected a loading dose of 600 mg on day one followed by 200 mg for daily maintenance dose.

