### 7.4.2 Analysis of the Primary Efficacy Endpoint(s)

Detection of SARS-CoV-2 RNA by PCR will be the primary endpoint and will be compared between treatment groups (prophylaxis vs. no prophylaxis). Positive SARS-CoV-2 will be defined as a binomial variable (i.e., positive SARS-CoV-2 or no positive SARS-CoV-2) and analyzed using Wilcoxon rank analysis. Potential confounders of the primary endpoint will be addressed by using standard statistical matching techniques, such as propensity score matching, and logistical regression to assess for confounding by exposure risk, demographic factors and comorbidities that are known or suspected to affect the likelihood of developing SARS-CoV-2 infection.

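### The visible eligibility criteria do not clearly exclude non-study hydroxychloroquine and set no look-back for recent use, so the no-prophylaxis group can include exposed people

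*Combined protocol and SAP*

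**What the plan says.** Three exclusions in protocol section 4.2.1.2 come near the issue:

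- Criterion 4: "Current medications exclude concomitant use of HCQ, for example anti-arrhythmic agents, digoxin, cyclosporin, cimetidine, or tamoxifen".
- Criterion 5: "Concomitant use of other anti-malarial treatment or chemoprophylaxis".
- Criterion 12: "Use of any investigational or non-registered drug or vaccine within 30 days preceding the first dose of the study drugs". This criterion also reaches such products if a participant intends to take them while enrolled, and it allows case-by-case exceptions to the washout.

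The IND Exemption text in section 1 states that "HCQ is lawfully marketed in the United States". The dose rationale (4.7.1.1) states: "Hydroxychloroquine is a long-acting drug (elimination half-life:50 days".

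The control group is described in more than one way. Section 4.2.1 has "Group B: up to 75 (HCW who choose not to be provided HCQ"; the population row of the Protocol Summary and section 5.2.3 use equivalent wording. Sections 5.2.2 and 7.2 describe people who decide against taking HCQ. Section 7.4.2 says the primary endpoint is "compared between treatment groups (prophylaxis vs. no prophylaxis".

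After enrollment, one withdrawal reason in section 4.6 is "Participant starts disallowed medication (Group A only". Section 5.2.3 provides for a move from Group B to study drug. Section 7.3 puts all enrolled participants in the primary analysis set.

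**The concern.** The primary objective is a contrast between HCQ and no HCQ, in groups that people choose for themselves. That contrast needs controls who are free of the drug. The documents make outside users foreseeable: sections 4.2.1.3 and 4.7.1.1 describe HCQ use in lupus and rheumatic disease, and section 4.7.1.3 mentions patients with existing indications. A worker who already has a prescription also has an obvious reason to decline the study supply, and so to land in Group B.

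If exposed people are counted as controls, any true drug effect is diluted. Group B is capped at 75, so a few such people are a noticeable share. The same gap lets a current user enter Group A without the visible text identifying it. The documents do not say how that case is handled, and the sponsor should state it.

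**Working it through.** **1. Do the criteria reach non-study HCQ?**

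| Provision | Current non-study HCQ | Recent HCQ, now stopped |
|---|---|---|
| Criterion 4 | Names drugs that cannot be combined with HCQ, not HCQ itself | No |
| Criterion 5 | Limited to other anti-malarials; criterion 1 uses the word other to mean other than HCQ | No; concomitant use only |
| Criterion 12 | Only if taken as an investigational product, since HCQ is marketed | Same limit; the 30 days run back from a first study dose, which a Group B member who never switches does not take |
| Section 4.6, disallowed medication | Group A only | Not applicable |
| Section 5.2.3 | Covers switches to study drug only | Not applicable |

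No row clearly covers HCQ prescribed for autoimmune disease, HCQ prescribed off label elsewhere, or recent use of either.

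**2. How long does exposure last?** Input: half-life 50 days (4.7.1.1). Assumption: simple first-order decay. Fraction remaining = 0.5^(t/50).

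- 30 days: 0.5^0.6 = 0.66
- 60 days: 0.5^1.2 = 0.44
- 90 days: 0.5^1.8 = 0.29
- 180 days: 0.5^3.6 = 0.08

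Someone who stopped 30 days before entry would start follow-up with about 66% of the earlier level. At day 90 (120 days after stopping) about 0.5^2.4 = 19% would be left.

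**3. The plan's own figure.** Section 7.5 gives 80% power for about 15 points (35% against 20%) with 230 treated and 120 controls, two-sided 0.05. The pooled normal approximation is power = Φ[(|p1 − p2| − 1.96·SE0)/SE1]. SE0 uses the pooled proportion (42 + 46)/350 = 0.2514, giving 0.0489. SE1 uses the separate proportions, giving 0.0509. Power = Φ[(0.15 − 0.0958)/0.0509] = 85.7%, so the stated 80% is not reproduced exactly. The detectable difference from a 35% control rate is 0.140, or 0.145 with a continuity correction, which rounds to the stated 0.15. The plan is slightly conservative here. That is a separate matter and does not affect this point.

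**4. Dilution.** Let c be the share of controls with the full HCQ effect. The documents give no value, so c is an assumption shown as a range. Control rate = 0.35 − 0.15c, so difference = 15 × (1 − c) points.

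| c | Difference (points) | Power, 230/120 | Power, 275/75 (caps) |
|---|---|---|---|
| 0 | 15.0 | 85.7% | 75.9% |
| 5% | 14.3 | 82.3% | 72.0% |
| 10% | 13.5 | 78.5% | 67.9% |
| 20% | 12.0 | 69.5% | 58.9% |

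With 75 controls, 4 exposed people are 4/75 = 5.3%, and 20% means 15 people. For people who stopped recently the loss shown is an upper bound: it credits them with the full effect throughout, while step 2 shows their level falling.

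**The case against.** The strongest reply has four parts.

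*Group B is already defined by exposure.* Sections 5.2.2 and 7.2 speak of not taking HCQ, and a worker on HCQ for lupus does not fit that naturally. This stands in part. A reader might infer from section 4.2.1 alone that Group B is defined only by declining the study supply; the other sections do not support that. What remains is an inconsistency.

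*The criteria are not empty.* Criterion 5 already bars current chloroquine used as an anti-malarial, and its word other could be read as other than study drug. Criterion 12 could catch HCQ from another trial. Criterion 4 lists examples only. It would therefore be too strong to say that nothing in the criteria keeps users out. But even the generous reading of criterion 5 does not clearly reach HCQ taken for autoimmune disease, and it sets no look-back.

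*Other documents may close the gap.* The medication appendix (4.7.1), the screening form (4.3, 5.2.3) and the added survey questions (5.1.1, 5.2.2) are not reproduced, and section 5.2.1 schedules a baseline health history. A reader might infer that outside use goes unrecorded; that cannot be concluded. The supportable statement is that the visible text does not specify recording it. Even if the appendix lists HCQ, the stated withdrawal rule for disallowed medication would still apply to Group A only.

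*The effect may be negligible and its direction uncertain.* This stands as a limit on size. At 5% the loss is 0.75 points. Section 1 allows that HCQ may lower, raise or not change infection risk; with no effect there is nothing to dilute. Outside users may also differ in baseline risk, so the net bias need not point toward zero.

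**Conclusion.** The concern holds in limited form. On the visible text, current non-study HCQ use is not clearly excluded, recent use of the marketed drug has no look-back despite the stated 50-day half-life, the Group B definition is inconsistent, and an outside start in Group B is not addressed. Exposed people can therefore be analysed as controls.

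The size is unknown. Under the 35% against 20% scenario, the loss is 0.75, 1.5 or 3.0 points if 5%, 10% or 20% of controls had the full effect. This rests on assumed shares, on an exposed control gaining no more than a Group A member, and on otherwise equal infection risk. The case for acting is that the gap is cheap to close, not that the bias has been shown to be large.

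**What to change.** 1. Add an explicit exclusion for both groups: current non-study HCQ or chloroquine for any indication, and recent use within a look-back that the sponsor sets and justifies from its own half-life figure. Anchor it to enrollment, so that it also works for Group B.
2. Reconcile the Group B wording in the Protocol Summary and sections 4.2.1, 5.2.2, 5.2.3 and 7.2 to one definition: not taking HCQ from any source.
3. Ask about non-study HCQ and chloroquine in both groups at pre-screening, in the study-specific survey questions and at the 30, 60 and 90 day contacts, with start and stop dates. If the screening form, appendix or survey already does this, cite it in the protocol.
4. State in section 7 that an outside start in Group B is analysed as a dated change of exposure or, at the least, in a pre-specified sensitivity analysis.

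The cost is one eligibility line, one screening question, one survey item and a short analysis paragraph. A few otherwise eligible workers would be excluded.

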#### **4.2.1.3 Vulnerable Subjects**

This study will enroll employees of UNM HEALTH SYSTEM. Employees (For example: MD/DO, NP, RN, PA, Respiratory Therapists) recruited as research subjects may be more vulnerable to undue influence or coercion because of the possibility that they may perceive employment or other benefits as dependent upon their participation in research. In addition, UNM HEALTH SYSTEMS employees may experience increased risk of invasion of privacy or loss of confidentiality. To minimize these risks, employees will be allowed to self-identify as interested in being contacted for study participation after recruitment materials are sent to potentially eligible employees. Employees may then reach out to the research team to learn more about the study and if enrolled (if employee elects to participate), informed consent will be performed by a study team member with no direct supervisory or evaluation responsibilities. Additionally, at time of enrollment, the study team member will emphasize that participation is voluntary and refusal to participate will not affect employment or job performance evaluation. All identifying information for employees will be kept strictly confidential following the data security provisions outlined in this protocol.

Pregnant and /or lactating women will not be excluded from this study. HCQ is a standard of care for management of lupus and rheumatic diseases in pregnant women. There is an absence of data that the drug increases the rate of miscarriages or teratogenicity. Additionally, the drug is approved to be used in pregnant women to treat autoimmune disease and there is consensus in the scientific community that the drug does not have adverse effects on the fetus [13-16]. Each participant providing consent is fully informed regarding the reasonably foreseeable impact of the research on the fetus or neonate. No inducements, monetary or otherwise, will be offered to terminate a pregnancy; Individuals engaged in the research will have no part in any decisions as to the timing, method, or procedures used to terminate a pregnancy; and Individuals engaged in the research will have no part in determining the viability of a neonate. A systematic review determined that HCQ use was not associated with any increased risk of congenital defects, spontaneous abortions, fetal death, pre-maturity or decreased numbers of live births in patients with auto-immune diseases. (Systematic review of hydroxychloroquine use in pregnant patients with autoimmune diseases, *Pediatric Rheumatol Online J.* 2009; 7: 9).

Additionally, *Arthritis Rheum.* 2003 Nov;48(11):3207-11 published. Safety of hydroxychloroquine in pregnant patients with connective tissue diseases: a study of one hundred thirty-three cases compared with a control group. Hydroxychloroquine in systemic lupus erythematosus and rheumatoid arthritis and its safety in pregnancy. Appeared in *Expert Opin Drug Saf.* 2011 Sep;10(5):705-14.

#### **4.3 Strategies for Recruitment**

Study participants will be recruited using an HRRC approved email blast that will be sent to the departments that are specific to the desired study population. We will be using UNM HEALTH SYSTEMSC listservs which will be chosen based on their pertinence to the study population. The email blast will direct interested HCW to a study team email address for further study information. Upon email contact from potential participant, study team will reply asking for a time to speak over the phone to discuss pre-screening criteria. In the phone call, pre-screening questions will be asked and documented on paper.

If potential participant is not eligible, participant cannot enroll in the study, and paper pre-screening form will be destroyed. If participant is eligible, paper pre-screening form will be kept in participant's study records and will serve as the screening source document. E-consent will be sent. Participant and study team will go over e-consent, and participant will e-sign. Word of mouth will also be used to recruit participants into the study.

#### **4.4 Duration of Study Participation**

- Study period: up to 90 days

#### **4.5 Total Number of Participants and Sites**

We expect to enroll up to 350 participants at UNM HEALTH SYSTEM. Subject visits will be conducted remotely after the Screen and Enrollment visit.

## 4.6 Participant Withdrawal or Termination

Reasons for early Withdrawal or Termination

- Participants become PCR-confirmed SARS-CoV-2 status
- Participant starts disallowed medication (Group A only)
- Advent of an adverse event which necessitates discontinuation of HCQ (Group A only, see section 6)
- Participant decides to withdraw from the study
- PI discontinues participation due to safety concerns
- Participant decides to withdraw consent
- Participant's primary care provider determines the study is not in participant's best interest
- PI decides to withdraw participant due to non-compliance

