**Protocol Summary**

Title	Off label study to evaluate the efficacy of hydroxychloroquine as prophylaxis to prevent severe acute respiratory syndrome coronavirus 2 (SARS-CoV-2) infection among Health Care Workers (HCWs) who are at high risk of occupational exposure to SARS-CoV-2 Short Study Title: COVID-19 HCWP HCQ Study
Brief Summary	The HCW Prophylaxis (HCWP) Study, single, open and off label intervention study. Up to 350 participants will be assigned to group that takes HCQ or group that opts to not take study medication. Participants will be UNM HEALTH SYSTEM HCW at high risk for occupational exposure to SARS-CoV-2. Study timepoints will include Day 1 screening/enrollment, 30 day, 60 day, and 90 day assessments. Questionnaires will be collected in all timepoints.
Phase	Off label use of HCQ
Primary Objectives	To evaluate the efficacy of hydroxychloroquine (HCQ) for prophylaxis (HCWP) to prevent severe acute respiratory syndrome coronavirus 2 (SARS-CoV-2) infection among Health Care Workers High Risk of Occupational Exposure to SARS-CoV-2
Methodology	The Health Care Worker Prophylaxis (HCWP) Study, single, open and off label intervention study
Primary Endpoint	Number of HCW who test positive for SARS-CoV-2 while in the trial as determined by polymerase chain reaction assays from standard of care swaps.
Study Duration	12 months
Participant Duration	Participant Study period: up to 90 days for both groups, inclusive of those who elect to convert from Group B to Group A.
Duration of IP administration	Up to 90 days
Population	Total number of participants: Up to 350 UNM HEALTH SYSTEM health care workers with high risk of occupational exposure to SARS-CoV-2 Group A: up to 275 (HCW choose to be provided HCQ) Group B: up to 75 (HCW choose not to be provided HCQ)
Study Sites	UNM HEALTH SYSTEMS
Number of participants	Up to 350
Description of Study Agent/Procedure	Hydroxychloroquine- oral administration 
 
• Duration: up to 90 days or until meeting study termination criteria
 
• Loading dose: 600 mg once for the first day
 
• Maintenance dose: 200 mg, daily
 
 
Hydroxychloroquine is licensed for the chemoprophylaxis and treatment of malaria and as a disease modifying antirheumatic drug. It has a long history of being safe and well tolerated at typical doses. HCQ has antiviral activity in vitro against coronaviruses, and specifically Covid-19.

Key Procedures	Questionnaires

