### 3 Objectives

Primary Objective	Primary Endpoint
To evaluate the efficacy of hydroxychloroquine (HCQ) for prophylaxis to prevent severe acute respiratory syndrome coronavirus 2 (SARS-CoV-2) infection among HCWs at high risk of occupational exposure to SARS-CoV-2 compared to eligible cohort that declines treatment	Frequency of infection with SARS-CoV-2 as determined by positive PCR for the virus on standard diagnostic tests.
Secondary Objectives	Secondary Endpoints
1. To characterize whether high-risk HCW who test positive for SARS-CoV-2 have an asymptomatic infection or report symptoms of COVID-19 in the 4 weeks preceding positive SARS-CoV-2	1. Symptom questionnaires performed once daily as currently mandated for HCW in high risk settings within UNMHS.
2. Determine role of occupational health exposure risk level on subsequent conversion frequency (mild-moderate-severe)	2. Online survey required once daily for all at risk HCW (existing document)
3. To assess the severity of any SARS-CoV-2 infection after prophylactic treatment with hydroxychloroquine.	3. Symptom questionnaires, Hospital admission rate, ICU admission rate, Mortality rate, PSI score of respiratory compromise
4. To assess the tolerability of hydroxychloroquine prophylaxis of SARS-CoV-2 in this population	4. Incidence of AEs or SAEs related to HCQ at study termination.
Exploratory Objectives	Exploratory Endpoints
1. To determine whether hydroxychloroquine reduces time lost from work	1. Days away from work
2. To assess the compliance of hydroxychloroquine prophylaxis	2. Frequency of missing dose
3. To assess whether HCQ benefits are different for specific AGPs or exposure on certain covid units (MICU v. ED v. covid rule out unit)	3. Frequency of positive test for SARS-CoV-2 related to AGP's or specific Covid-19 units.
4. To compare seroconversion between HCQ-treated and HCQ-untreated subjects on blood or plasma specimens.	4. Serological analyses at 4 times points (baseline, 30,60 and 90 days of study enrollment---with a 7-day window after each time point to complete analyses)

5. Metagenomic next generation sequencing of SARS-CoV-2 isolates detected in subjects	5. Sequence of viral isolates compared to published genomes and community-circulating SARS-CoV-2
---	--

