#### 4.7.1.2 Administration

- Loading dose: 600 mg, oral, 1 day
- Maintenance dose: 200 mg, oral, daily, for 90 days

The study will follow the study agent's labeling guidelines except the dosing schedule selected as described above.

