### 5.2 Study Schedule

#### 5.2.1 Schematic of Study Design

##### Schematic of Study Design

**Schedules of Activities for COVID-19 HCWP HCW HCQ Study**

Task	Screening/ Baseline	Daily (existing required survey)	30 Day (± 7days)	60 Day (± 7days)	90 Day (± 7days)	Early Termination or Clinically Suspected SARS- CoV-2
Consent	X					
Health history	X					
Exposure Survey (online)	X	X				X
Swab* for SARS-CoV-2 and plasma/serum sample	X		X	X	X	X
Hydroxychloroquine dosing initiation	X					
Adverse Events		X	X	X	X	X

\*Lab has confirmed ability to test samples from week over next weekend. Estimate up to 50 total per week (25 Sat, 25 Sun). Lab has also agreed to bank plasma and serum samples for delayed analysis.

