### **7.3 Analysis Datasets**

The primary analysis data set will consist of positive SARS-CoV-2 outcomes for all enrolled participants. Sensitivity analyses will be conducted using the subset of HCQ participants who complete their entire course of treatment.

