### 7.4.3 Analysis of the Secondary Endpoint(s)

Secondary endpoints include symptoms reported over time via questionnaires, as well as other clinical endpoints such as hospital admission, ICU admission, and mortality. These binary clinical outcomes will be analyzed in a manner similar to that described above for the primary endpoint. Symptoms will be included as predictor variables. Antibody titers for SARS-CoV-2, measured as an exploratory endpoint in serum or plasma samples, will also be analyzed as binomial values. Positive values will be defined as a four-fold or greater increase in IgG antibody titers compared to baseline. Other descriptive analyses will be provided of the antibody titer results, including geometric mean, median, standard deviation, and titer range.

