## 7.5 Sample Size

The total sample size will be approximately 350 participants. We do not know in advance how many will opt to take or not take HCQ. The table below provides the detectable difference in positive SARS-CoV-2 rate for different proportions of participants in the treated and control groups. For example, if two-thirds of the sample opt to take HCQ, we will have 80% power to detect a difference in positive SARS-CoV-2 rate of approximately 15 percentage points (e.g., a 35% PCR positivity rate in the control group and a 20% PCR positivity rate in the HCQ group). These calculations assume a two-sided Type I error rate of 0.05. The exploratory endpoints remain independent of enrollment in Group A vs. Group B.

Treatment Group	Control Group	Detectable difference
175	175	0.14
230	120	0.15
260	90	0.17

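### A positive PCR ends participation (section 4.6), so the HCQ completer sensitivity analysis in section 7.3 is selected on the outcome in Group A only

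*Combined protocol and SAP*

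**What the plan says.** Section 4.6 gives one list of reasons for early withdrawal or termination, and "Participants become PCR-confirmed SARS-CoV-2 status" is on it. Two other items on the list are marked as applying to Group A only. This one is not, so it also ends participation for untreated Group B and cannot be read as a drug-stopping rule alone.

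Section 7.3 bases the primary analysis on all enrolled participants and adds: "Sensitivity analyses will be conducted using the subset of HCQ participants who complete their entire course of treatment". It names no comparator and no method for that analysis, and it does not define the course.

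Two other places bear on the course. Section 4.7.1.2 has "Maintenance dose: 200 mg, oral, daily, for 90 days". The Protocol Summary has "Duration: up to 90 days or until meeting study termination criteria".

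On data after infection, section 7.4.3 defines seropositivity thus: "Positive values will be defined as a four-fold or greater increase in IgG antibody titers compared to baseline". The schedule of activities has a row "Swab* for SARS-CoV-2 and plasma/serum sample" at baseline, days 30, 60 and 90, and at early termination or clinically suspected infection. Section 5.2.4 describes the early termination visit as a questionnaire and a nasal swab, with no blood. No scheduled visit after termination is described.

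**The concern.** A completer set should be defined by what participants did with the drug. Here the primary outcome itself removes people from it. An HCQ participant who is infected and detected before day 90 leaves the study and so does not finish a 90-day course. An equally infected control still counts as an event. The completer rate in Group A is therefore pushed down by construction.

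This matters because it is the only analysis that the plan labels a sensitivity analysis, in an open-label comparison of self-selected groups. If it agreed with a favourable primary result, it could be read as confirmation when part or all of the agreement came from the definition.

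A smaller matter is that the same rule leaves no scheduled serum after the termination contact, in the very participants in whom a rise in IgG is expected.

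**Working it through.** **The plan's own figure.** Section 7.5 states 80% power for "a 35% PCR positivity rate in the control group and a 20% PCR positivity rate in the HCQ group" with two-thirds on HCQ (230/120). The pooled two-proportion formula gives 85.7%. The unpooled version gives 83.8%, the continuity-corrected 82.7% and Fisher's exact test 84.7%. The stated figure is conservative, and nothing below depends on it. The 35% and 20% rates are used only as illustrations.

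**Inputs.** Group sizes 275/75 are the caps in section 4.2.1. Swabs at days 30, 60 and 90 are from section 5.3. The two-sided 0.05 level is from section 7.4.1. The rank test on a binary outcome is from section 7.4.2. Assumed here: no drug effect, detection only at scheduled swabs, a 90-day course, a day-90 positive counted as a completer, and all of Group B as an unadjusted comparator.

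**Completer rate.** Let R be the 90-day risk and m1, m2, m3 the shares of infections detected at days 30, 60 and 90.

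- Share of HCQ positives dropped = m1 + m2
- Fraction completing = 1 − R(m1 + m2)
- Observed completer rate = R·m3 / [1 − R(m1 + m2)]

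With a constant hazard, q = 1 − (1 − R)^(1/3) per 30 days, the fraction completing is (1 − R)^(2/3), and the completer rate is q. For R = 0.35, q = 0.134 and the fraction completing is 0.750. Of 275 HCQ participants about 96 are positive and 69 of them are dropped, which leaves 28 among 206 (13.4%).

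With a 20/30/50 split: 0.175 / (1 − 0.175) = 21.2%. With 10/20/70: 0.245 / (1 − 0.105) = 27.4%.

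**Chance of a significant result favouring HCQ.** The number of completers is enumerated as binomial(275, fraction completing), then the positives among completers and among 75 controls. The test rejects when the tie-corrected rank statistic passes its two-sided 0.05 limit in HCQ's favour.

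| True risk, both groups | Timing | HCQ positives dropped | Completer rate | RR | Chance (nominal 2.5%) |
|---|---|---|---|---|---|
| 35% | constant hazard | 71% | 13.4% | 0.38 | 97% |
| 35% | 20/30/50 | 50% | 21.2% | 0.61 | 66% |
| 35% | 10/20/70 | 30% | 27.4% | 0.78 | 25% |
| 10% (assumed) | constant hazard | 68% | 3.45% | 0.35 | 60% |
| 10% (assumed) | 20/30/50 | 50% | 5.3% | 0.53 | 33% |
| 10% (assumed) | 10/20/70 | 30% | 7.2% | 0.72 | 14% |

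**Symptom-driven swabs.** The schedule allows a swab on clinical suspicion, so some month-3 infections would be confirmed before day 90. If 40% were, the share dropped at R = 0.35 rises from 71% to 83% (constant hazard) and from 30% to 58% (10/20/70). The completer rate falls to 8.5% and 18.4%. If all were, no positives remain among completers.

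**Check of the remedy.** If completion means HCQ taken as planned up to the earlier of first positive PCR and the planned end of the course, all 96 positives among 275 stay. The rate is 35% and the RR is 1.

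**Serum.** At the section 7.5 rates with 230/120 and a constant hazard, Group B has about 16.1, 13.9 and 12.0 positives in the three months, and Group A 16.5, 15.3 and 14.2 (88 in all).

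- Detection at scheduled swabs loses two later samples per day-30 positive and one per day-60 positive: (2×16.1 + 13.9) + (2×16.5 + 15.3) ≈ 94.
- Immediate detection loses three, two and one: (3×16.1 + 2×13.9 + 12.0) + (3×16.5 + 2×15.3 + 14.2) ≈ 182, with at most one termination sample per person in exchange.
- At an assumed 10% risk in both groups, the same sums give 36 to 71.

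**The case against.** The best defence is the Protocol Summary. If the course runs until a termination criterion is met, a PCR exit has completed it and the selection disappears. That reading is open. But it would equally count adverse-event and other exits as complete, and the set would no longer describe completers. Section 4.7.1.2 says 90 days without that qualification. The ambiguity has to be settled before analysis.

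Second, section 7.3 names no comparator, and section 7.4.2 plans matching and logistic regression. The figures above are for an unadjusted comparison with all of Group B, so they are not a forecast. Adjustment for baseline factors would not undo selection on the outcome itself, though a Group B restricted in the same way would change the result. That is a reason to name the comparator.

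Third, a reader might infer that data collection ceases once someone is infected. The documents do not support that. Section 6.1 treats intercurrent illness as an adverse event. Section 6.2 makes admission and death serious adverse events. Section 6.4 collects events for 7 or 30 days after participation and follows them to resolution or stabilization. Much of "Symptom questionnaires, Hospital admission rate, ICU admission rate, Mortality rate, PSI score of respiratory compromise" is therefore still covered. PSI and days away from work are not named in the schedule at all, before or after infection, so their absence cannot be laid on section 4.6. The daily survey is required by the employer regardless, although its linkage to the study after exit is not stated. The clear loss is the later serum, which serves an exploratory endpoint.

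**Conclusion.** The point holds for section 7.3. On the 90-day reading, the HCQ completer set is conditioned on the outcome in one group only, and the bias favours HCQ in every case examined.

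Its size is not fixed. A reader might infer that the analysis would show a reduction of about 60%, or that it drops most HCQ-group positives. Those statements need a roughly constant hazard and, for the 60%, an unadjusted comparison with all of Group B. With later infections and scheduled swabs only, half or 30% of positives are dropped and the RR is 0.61 or 0.78 at a 35% risk. Even the mildest case in the table gives a 14% chance of a false significant result, several times the nominal 2.5%.

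The primary analysis is not affected: it includes all enrolled participants, and the endpoint has already occurred when the participant leaves. Secondary objective 1, which looks at the four weeks before the positive test, is also unaffected. The missing serum after infection (about 94 to 182 samples at illustrative rates) is a lesser point. The whole is worth amending, but it does not undermine the main comparison.

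**What to change.** 1. **Section 7.3.** Define the completer set as participants who took HCQ as planned up to the earlier of first positive PCR and the planned end of their course. State the rule for those who switch from Group B to Group A: section 5.2.3 gives them the section 4.7.1.2 regimen, while the Protocol Summary limits their participation to 90 days in total, so a late switcher could not complete 90 days of drug. Name the Group B comparator. Cost: a few sentences. Downside: early positives are slightly over-included, because they had less time to become non-adherent.

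2. **Section 4.6.** Record stopping HCQ separately from leaving follow-up. Keep PCR-positive participants in the already scheduled surveys and serum to day 90, unless they withdraw or the investigator or primary care provider ends participation. Cost: an amendment and modest extra contact and sampling, of the order of the serum counts above.

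3. **Reconciliation.** Make the Protocol Summary and sections 4.6, 4.7.1.2 and 7.3 agree on what ends the course, and make section 5.2.4 and the schedule agree on the termination blood sample. The Protocol Summary ties HCQ duration to the termination criteria, so a change to section 4.6 touches that wording. The sponsor must reconcile the passages, and no drug-stopping rule is proposed here.

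A time-at-risk analysis would be a reasonable addition but is optional.
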